6.1 General Design

This will be a prospective clinical trial designed to evaluate the incremental benefit of virtual FFR measured from CCTA, compared to invasive FFR and CCTA for the detection of flow-limiting coronary stenosis, as defined by invasive FFR ≤ 0.8 and vessel diameter of $\geq 2\text{mm}$.

572 consecutive patients who present to Lenox Hill Hospital Outpatient Clinics for CCTA due to chest pain or stable angina over a ten month period and meeting the study inclusion criteria are eligible for the study (Figure 1). Our team will employ CCTA-appropriateness criteria to ensure proper selection of patients, derived from the Appropriate Use Criteria for Cardiac Computed Tomography published in 2010 and jointly authored by multiple societies including ACCF, SCCT, and ACR [10]. FFR-CT measurements will be performed by a core laboratory in a blinded fashion. All eligible patients will undergo 64-slice or greater multi detector CCTA and CT-FFR measurements. The severity of the stenosis will be determined on site by level III CCTA readers. Patients with obstructive lesions of (30% to 100% stenosis) will receive Stress-MPI, per SOC protocol, and CT-FFR. Patients with positive Stress-MPI and CCTA (50% - 70%) or positive CCTA (71% to 100%) will undergo ICA with invasive FFR measurement in accordance to accepted guidelines and established practice standard. Those patients with invasively measured FFR ≤ 0.8 and with vessel diameter of $\geq 2\text{mm}$, or those who require revascularizations based on invasively estimated stenosis severity will be considered to have flow-limiting obstructive CAD, while the rest will be considered to have non-flow limiting obstructive CAD (if also $>50\%$ stenosis on ICA). If stenosis severity turns out to be $< 50\%$ after ICA (the gold standard), we will conclude that these patients have non-obstructive CAD. (Figure 1). Patients with 30% to 49% obstructive disease, according to CCTA, will be referred to optimal follow up care only. Any in this group who have positive CT-FFR will return for

ICA with invasive FFR measurement, and follow the protocol for those with 50% to 100% obstruction.

Figure 1:

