6.2 Primary Study Endpoints

Defining an event as performance of ICA when no intervention is necessary, we expect to compare event rates for patients treated with CCTA and FFR-CT, using t-tests and a multivariate, risk adjusted 90 day hazard model with 95% confidence interval. Our null hypothesis is that outcomes will not vary regardless of which testing is used to assess

obstructive disease. Our alternative hypothesis is that evaluation with FFR-CT as oppose to CCTA will change the event rate. We will also correlate noninvasive and invasive FFR studies.

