8.3 Method for Assigning Subjects to Treatment Groups

This is not a randomized study. Treatment assignments will follow the clinical protocol.

Once the CCTA results are interpreted by the physician, the physician will order CT-FFR exams for patients whose level of stenosis by CCTA standards is 30% to 100%.

If CT-FFR is positive patients will be referred for Cardiac Catheterization and invasive FFR.

If CT-FFR is negative, and level of obstruction is 30 to 49% by CCTA standards, patients will be referred to optimal medical care.

If CT-FFR is negative and level of obstruction is 50% to 70% by CCTA standards, patient will be referred for stress MPI. If stress MPI is positive patients will be referred for Cardiac Cath and invasive FFR. If stress MPI is negative, patients will be referred to optimal medical care.

If the patient has had a stress MPI within one year of the CCTA exam and the CCTA exam result is 50% to 70% obstructive, the physician will rely on the prior stress testing result, rather than repeating the stress test. If the stress testing results was negative, the patient will be referred to optimal medical care. If, in the investigator's opinion, the results indicate that the patient is at increased risk of obstructive disease, when considered with the CCTA findings, the patient will be referred to Cardiac Cath and Invasive FFR.

If CT-FFR is negative and level of obstruction is 70% to 100% by CCTA standard, patient will be referred to Cardiac Cath and Invasive FFR.

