*Patients who have borderline obstructive disease (50% to 70% stenosis) who have negative CT-FFR will be referred for Stress MPI to confirm, unless the patient has had stress testing within a year of the CCTA. This is an accepted practice as part of the standard of care at Lenox Hill Hospital. If the stress test is negative, the patient will be referred to his/her physician for follow-up. If the stress test is positive, the patient will be referred to Invasive Coronary Angiography for Invasive FFR and diagnostic cardiac catheterization. If the patient has had a history of negative stress testing within a year of the CCTA, then the patient will be referred to his/her physician for follow-up. If the patient's prior stress test had findings that, in the investigator's opinion, increase the patient's risk of obstructive disease when viewed with the CCTA findings, the patient will be referred to Invasive Coronary Angiography for diagnostic cardiac catheterization and Invasive FFR. This is an accepted practice as part of the standard of care at Lenox Hill Hospital.**

Patients who have borderline obstructive disease (50% to 70% stenosis) who have positive FFR will be referred for Invasive Coronary Angiography for Invasive FFR and diagnostic

*cardiac catheterization. This is an accepted practice as part of the standard of care at Lenox Hill Hospital. **

Patients with 71% or greater stenosis will be referred for Invasive Coronary Angiography for Invasive FFR and diagnostic cardiac catheterization. This is an accepted practice as part of the standard of care at Lenox Hill Hospital.

**In current standard of care practice at Lenox Hill Hospital, for borderline obstructive coronary disease, the decisions as to whether to proceed with stress testing or refer to invasive coronary angiography is left to the medical discretion of the attending cardiologist.*

Invasive Coronary Angiography and Invasive FFR are considered to be the gold standard procedures for evaluation of obstructive coronary artery disease. Patients deemed to be at high risk for obstructive disease based on CCTA or Stress testing are referred for invasive testing to determine whether cardiac intervention consisting of Percutaneous Coronary Intervention or Coronary Artery Bypass Graft is necessary.

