14.1 Sample Size Determination

Based on data from Stony Brook and confidential data HeartFlow reported from providers who have been using CT-FFR in a similar manner as we propose for this study, we estimated that about 60% of stable chest pain patients who had CCTA were diagnosed with coronary stenosis of 30% to 90% and received CT-FFR. Of these patients, about 35% had an ICA test, and 14% of those had a negative ICA test result (i.e. the false-positive rate of CCTA+CT-FFR was 14%). A sample of 121 patients who received ICA will yield 80% statistical power of detecting a 60% reduction in the false-positive rate (from 14% to 6%), based on a two-sided one sample Chi-square test with 0.05 significance level. Assuming a similar prevalence of flow-limiting obstructive CAD and assuming that similar proportions of stable chest pain patients who had CCTA will receive CCT-FFR and then ICA, 576 stable chest pain patients who had CCTA need to be complete the clinical trial. In order to target 576 subjects completing the trial, we estimate that number of patients, it will be necessary to 594, because 18 patients who enrolled were screen failures.

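### The primary comparison ignores CCTA stenosis band, so a cohort difference at 71-100%, where CT-FFR cannot change referral, would be read as a CT-FFR effect

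*Combined protocol and SAP*

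**What the plan says.** **Primary comparison.** Section 6.2 defines the event as an ICA performed when no intervention is needed and states: "we expect to compare event rates for patients treated with CCTA and FFR-CT, using t-tests". The same sentence adds a multivariate, risk-adjusted 90-day hazard model, with no covariates listed. Controls (sections 6.1, 7.4 and 9) are 2014-2018 catheterizations at the same hospital indicated by a positive stress test, a positive CCTA, or both.

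**Referral by CCTA band.**
- *71-100%.* Section 6.1: "or positive CCTA (71% to 100%) will undergo ICA with invasive FFR measurement in accordance to accepted guidelines and established practice standard". Section 8.3 gives the same outcome after a negative CT-FFR: "If CT-FFR is negative and level of obstruction is 70% to 100% by CCTA standard, patient will be referred to Cardiac Cath". Section 9: "Patients with 71% or greater stenosis will be referred for Invasive Coronary Angiography for Invasive FFR and diagnostic cardiac catheterization", described there as accepted standard care at the hospital.
- *50-70%.* Under sections 8.3 and 9, a positive CT-FFR leads to ICA. A negative one leads to stress MPI (or a prior stress result), which decides. Without CT-FFR, the choice between stress test and ICA is at the cardiologist's discretion.
- *30-49%.* The default in section 6.1 is follow-up care. A positive CT-FFR adds an ICA: "Any in this group who have positive CT-FFR will return for" it. Sections 10 and 11 expect very few such patients.

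**Sample size and covariates.** Section 14.1 sizes the trial on one undivided group: "121 patients who received ICA will yield 80% statistical power", "based on a two-sided one sample Chi-square test with 0.05 significance level". The only covariate list is in section 14.2, Aim 3 (return visits). It has no stenosis band.

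**The concern.** CT-FFR can reduce unnecessary catheterization only where its result can stop an ICA that would otherwise take place. At 71-100% it cannot, since the patient is catheterized either way, in the trial and in standard care. If negative ICAs in that band are rarer in the prospective cohort than in the charts, CT-FFR-guided referral is not the reason. Referral population, calendar period or the way results were classified from catheterization reports would be.

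The contrast is non-randomised, so such differences are plausible. Nothing stated in the primary analysis separates this band or adjusts for it, and the hypotheses in section 6.2 attribute any difference in outcome to the testing used. A different share of 71-100% cases in the two cohorts can have the same effect even if the rates within each band agree. The design contains a band in which the referral effect should be nil, and the plan does not use it to check comparability.

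**Working it through.** **1. The plan's own figure.** Inputs from section 14.1: p0 = 0.14, p1 = 0.06, two-sided alpha 0.05, power 80%, one-sample test.

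n = [1.96 × √(0.14 × 0.86) + 0.842 × √(0.06 × 0.94)]² / (0.14 − 0.06)² = 120.99, i.e. 121.

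With 60% receiving CT-FFR and 35% of those having ICA: 121 / (0.60 × 0.35) = 576.2, i.e. 576. Both figures reproduce. No band share enters.

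**2. Assumptions for the bias.** The documents give no control size, band shares or band rates. I assume 121 prospective and 500 control ICAs, half of each in the 71-100% band, and 14% negative in every control band. (Section 14.1 labels 14% as the CCTA + CT-FFR rate but uses it as the rate to be reduced; I use it in the second sense.) The test is the two-sample chi-square at two-sided 5%, with exact enumeration of the binomial outcomes. The tabulated quantity is the chance of a significant reduction.

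**3. Spurious difference in the 71-100% band only; no CT-FFR effect anywhere.** Prospective pooled rate = 0.5 × 14% + 0.5 × r.

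| r at 71-100% (controls 14%) | Pooled rate v 14% | False reduction |
|---|---|---|
| 14% | 14% | 2% |
| 10% | 12% | 7% |
| 8% | 11% | 12% |
| 4% | 9% | 29% |

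The plan's one-sample test against a fixed 14% gives 34% for the last row.

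**4. Different share of the band, identical band rates.** Assume 5% negative at 71-100% and 23% below it in both cohorts. Controls with a 50% share: 0.5 × 5% + 0.5 × 23% = 14%.
- Prospective share 70%: 0.7 × 5% + 0.3 × 23% = 10.4%; false reduction in about 16% of trials.
- Prospective share 80%: 0.8 × 5% + 0.2 × 23% = 8.6%; about 34%.

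This supposes that the shift comes from the referred population. If CT-FFR averts ICAs at 50-70%, that alone raises the 71-100% share among ICAs, and that part of a shift would be a real effect.

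**5. What the negative-control check would detect.** In the band alone (60 v 250 ICAs), 4% v 14% is flagged in about 64% of trials, 8% v 14% in about 21%, and 10% v 14% in about 10%. If only 50 controls have a known band, the 64% becomes 47%.

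**6. Precision by band.** For a true 14% v 6%, power is 72% over all ICAs (121 v 500) and 39% in a half-share 50-70% band (60 v 250). Pooling does not restore power for an effect confined to that band. The pooled rate is then 0.5 × 14% + 0.5 × 6% = 10%, and the one-sample test at 121 has 21% power.

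**The case against.** **The plan promises risk adjustment.** This is the best answer, since section 6.2 does commit to a multivariate model. But it names no covariates, and section 14.2 lists them only for return visits, without the band. Section 6.3 looks at results by level of obstruction, but as a secondary endpoint and not for the cohort contrast. A reader might infer that the plan is bound to credit a spurious difference to CT-FFR. That goes too far: the documents are silent on the band and do not rule out adjusting for it.

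**The 30-49% ICAs.** A reader might infer that these have no counterpart among controls and should leave the contrast. The documents do not support this. Controls can enter on a positive stress test alone with no band required, and section 6.1 mentions stress MPI for 30-100% lesions, so some may lie in this band. The trial's 30-49% ICAs are also caused by CT-FFR. Removing them would drop the band where CT-FFR can only add catheterizations, which favours CT-FFR.

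**Crediting CT-FFR only for a difference at 50-70%.** This too is tempting, but period, case mix and discretionary referral can differ in that band as well, and power there is low.

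**Is the expected difference at 71-100% zero?** It is for referral, not strictly for the event. Section 8.9.1 gives study cardiologists the CT-FFR images for their final recommendations, and a positive ICA can rest on a judgement that revascularization is required. CT-FFR could act through that judgement. This caveat stands.

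**The larger bias figures need large assumed differences.** That also stands, and the milder rows are shown for this reason.

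**Conclusion.** The point holds as a gap in the specification of the primary comparison. CT-FFR cannot change referral at 71-100%, and no stated primary analysis separates or adjusts for the band. A difference in rate or share there that has nothing to do with CT-FFR could pass for a CT-FFR effect.

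The size of the bias cannot be established from the documents. Under the assumptions above, the chance of a false reduction rises from about 2% to between 7% and 29% for a spurious rate difference in the band, and to 16% or 34% for the two assumed shifts in its share. These figures illustrate what is possible and do not estimate what will happen. The argument rests on the 71-100% band and does not depend on the 30-49% ICAs. The change should be made: it reduces an avoidable ambiguity at low cost, although it cannot make the historical comparison unconfounded.

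**What to change.** In sections 6.2 and 14.2:

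1. For each control ICA, abstract the indication and, where a CCTA preceded it, the CCTA stenosis band. Section 7.5 already provides for chart access to collect test results.
2. Name the band as a covariate in the risk-adjusted comparison, and report the negative-ICA share by band in both cohorts.
3. Prespecify the 71-100% band as a negative-control check. A difference there cannot come from CT-FFR-guided referral and signals that the cohorts are not comparable, subject to the caveat that CT-FFR images may influence the revascularization judgement. The absence of a significant difference does not establish comparability.
4. Keep the 30-49% CT-FFR-triggered ICAs in the whole-strategy comparison, and also list them separately as ICAs added by CT-FFR.
5. Keep the pooled rate and interpret it alongside the band results.
6. Report controls who entered on a stress test alone, with no CCTA band, as a separate group.

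Before this, the upper band boundary must be reconciled: sections 8.3 and 9.2 start it at 70%, sections 6.1 and 9 at 71%.

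The cost is revised wording and two abstracted items per control (indication and band), with no added patients or tests. The downside is imprecision within bands, as shown in the working, and more so if many controls have no CCTA.

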3.4 Clinical Data to Date

From 1/1/2009 to 3/31/2015 our team introduced and operated a CCTA Chest Pain triage program for low to intermediate risk patients at Stony Brook University Hospital ED and non-emergency outpatient services, the only tertiary care hospital in Suffolk County. Concurrently, we established a registry to monitor patient outcomes for all patients receiving CCTA at Stony Brook Medicine. Our registry contained nearly 15,000 patient CCTA procedures. Our major registry study established the effectiveness of CCTA as an imaging modality for evaluating ED chest pain in a cost efficient manner with a false negative rate less than 1% [5]. However, our registry reflects the poorer positive predictive values documented by other industry studies [6-8].

False positive workup results in the necessity of performing cardiac catheterization on patients at risk for obstructive disease based on assessment with current standard of care (combined screening with CCTA and stress MPI). Reduction in the rate of false positive testing would lead to reduction in risk from invasive procedures and radiation exposure to patients and reduced cost to the health care system.

Several medical institutions currently use HeartFlow CT-FFR as standard of care for evaluating obstructive disease. Generally, the standard of care at these institutions is to refer patients who are 30 to 100 percent obstructed by CCTA and who have reduction of flow \leq to 0.8 that is deemed to be medical significant by the attending cardiologist to Invasive FFR. HeartFlow has reported to us confidentially that this routine use of CT-FFR has resulted in a 54% reduction in false positive rate as compare to use of CCTA alone.

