In order to assess the primary endpoint of comparison of event rates for patients treated with CCTA and FFR-CT, we will perform a retrospective chart review of Invasive Coronary Angiograms performed at Lenox Hill Hospital from 2014 to 2018. We will specifically review Cardiac Catheterization reports to screen patients and record data for cases where the indication for Catheterization was (1) Positive stress test and/or (2) Positive CCTA. Based on the catheterization report we will determine whether the patient had obstructive coronary artery disease with/without flow limitation, in the same manner and following the same definitions as those used to categorize level of obstruction in subjects enrolled in the prospective cohort of the study. This data will be used as comparison/control group to assess trends and rates of invasive coronary catheterization when no intervention is necessary, in cases where CCTA and/or stress test without CT-FFR was used to determine the need for cardiac catheterization. Only the minimum amount of data required for a robust comparison of event rates will be collected.

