6.4 Primary Safety Endpoints

The study design evaluates the potential to substitute non-invasive for invasive FFR. Safety endpoints of the study include: 1. Evaluating the diagnostic accuracy of non-invasive FFR. If the end result demonstrates that the procedure is less accurate than invasive FFR, patients receiving this procedure, as an alternative to the current standard will be at greater risk. 2. Patients who undergo invasive procedures experience increased risk of infection or other comorbidities or complications, as compared to those who do not undergo invasive procedures. Therefore, if the noninvasive protocol results are not significantly different than the invasive results, patient safety might potentially be increased by using the noninvasive technology. 3. Noninvasive technology has the potential to reduce radiation exposure by reducing the number of invasive angiography and Stress MPI procedures necessary to complete patient evaluation. This increases patient safety relative to the adverse effects of radiation exposure.

7 Subject Selection and Withdrawal

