14.2 Statistical Methods

Statistical Aims

1. *To determine the sensitivity, specificity, positive predictive value (PPV) and negative predictive value (NPV) of the CCTA test (with or without stress MPI, as specified in Figure 1) + CT-FFR evaluation to identify chest pain patients with flow-limiting obstructive CAD. The ICA test will be used as gold standard.*
2. *To determine inter-observer reliability of CCTA and CCTA+CT-FFR test readings between an experienced and a non-experienced reader, and compare the results between CCTA and CCTA+CT-FFR; to determine the intra-observer reliability of CCTA and CCTA-FFR reading, for both the experienced and non-experienced reader, and for each reader compare the results between CCTA and CCTA+CT-FFR.*

3. To identify factors of return visit within 90 days in patients who had no ICA test or a negative ICA test result.

Outcome Variables

- *CCTA+CT-FFR test status (Positive/Negative). The test is deemed positive if ICA is required and negative if ICA is not required (see Figure 1).*
- *ICA (gold standard) test status (Positive / Negative). ICA is deemed positive if $FFR < 0.8$ and vessel diameter $>= 2\text{mm}$ or if the patient requires revascularizations based on invasively estimated stenosis severity. It is deemed negative otherwise.*
- *Return visit within 90 days (Y/N). Return visit is defined as patients who return for unplanned cardiac care, including emergency room visits, emergency hospital admissions, urgent percutaneous coronary intervention, coronary artery bypass graft, or acute myocardial infarction. Descriptive statistics (n, mean, median, standard deviation, IQR, frequencies and percentages) will be used to describe the demographic and clinical characteristics of the whole sample.*

For Aim 1, sensitivity, specificity, PPV, and NPV will be computed using the ICA result as the ‘true’ flow-limiting obstructive CAD status and the CCTA+CT-FFR test result as the ‘test’ status. Exact binomial 95% confidence intervals will be computed.

For Aim 2, inter- and intra-observer reliability for the CCTA and CCTA+CT-FFR tests will be assessed using Cohen’s Kappa coefficient. Dependent Kappa coefficients will be compared using a method developed by Donner et al .

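### The 2014-2018 control holds only patients who had an ICA, so the plan can compare the negative share among ICAs with history, but not unnecessary ICAs per patient evaluated or a 90-day hazard

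*Combined protocol and SAP*

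**What the plan says.** - **Endpoint (6.2).** The event is an ICA that turns out not to need an intervention. Event rates are to be compared between strategies by t-tests and a risk-adjusted 90-day hazard model. No denominator is given. The alternative hypothesis reads: "Our alternative hypothesis is that evaluation with FFR-CT as oppose to CCTA will change the event rate".
- **Control (6.1, repeated in 7.4 and 9).** ICAs performed from 2014 to 2018 are found from catheterization reports and kept if the indication was a positive stress test, a positive CCTA, or both. Their purpose: "This data will be used as comparison/control group to assess trends and rates of invasive coronary catheterization when no intervention is necessary". The consent-waiver request in 7.5 likewise describes people who had been catheterized.
- **Prospective cohort (6.1).** Consecutive outpatients enter when they present for CCTA, before any decision on ICA.
- **Sample size (14.1).** "A sample of 121 patients who received ICA will yield 80% statistical power of detecting a 60% reduction in the false-positive rate". The planning values are 14% and 6%, and the test is a one-sample chi-square, two-sided, at 0.05. The 14% is a share of patients who had ICA.
- **Accuracy analyses.** Section 6.2 adds: "We will also correlate noninvasive and invasive FFR studies". Section 6.4 lists: "Evaluating the diagnostic accuracy of non-invasive FFR". Sections 2 and 3.1 intend predictive values for each modality. In 14.2, however, Aim 1 uses one combined test status: "The test is deemed positive if ICA is required and negative if ICA is not required".
- **Expected benefit (10 and 11).** The investigators believe CT-FFR can markedly reduce diagnostic catheterizations that lead to no intervention.

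**The concern.** A rate per patient needs the patients who were evaluated and did not go to ICA. The cohort has them and the control does not. The endpoint section speaks of patients treated, the control supplies performed ICAs, and the sample size works per ICA. Two things are at stake. First, an analyst who follows 6.2 literally could set a rate per CCTA patient against a rate per ICA. Second, even with matched denominators, a change in the negative share could be reported as a change in the number of unnecessary catheterizations, which is the benefit that Sections 10 and 11 anticipate. The share alone does not show that.

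**Working it through.** **1. Reproduce the plan's figure.** One-sample formula with p0 = 0.14 and p1 = 0.06:

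n = [1.960·√(0.14·0.86) + 0.842·√(0.06·0.94)]² / 0.08² = 120.99, so 121 ICAs.

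With 60% of CCTA patients receiving CT-FFR and 35% of those having ICA (14.1), 121 / (0.60 × 0.35) = 576 CCTA patients. Both figures reproduce, and both rest on the negative share among performed ICAs.

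**2. Look for a control denominator.** None is planned. The annual volume of more than 1,000 CCTA scans in Section 5 is a recruitment figure and omits stress-test referrals, which the control includes. The registry in 3.4 belongs to another hospital and is not named as the control. The hazard model has the same gap, because every control patient has already had an ICA and none is at risk without one. The survival model in Aim 3 concerns return visits and is a separate matter.

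**3. What mixed denominators would do.** The cohort's planned ICA rate is 0.60 × 0.35 = 21% of CCTA patients. Suppose the negative share were 14% in both groups. The cohort rate per CCTA patient would be 0.21 × 14% = 2.94%, against 14% per ICA in the control. That is an apparent 79% reduction with no difference in yield. The plan does not say it will do this, but 6.2 does not exclude it.

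**4. How share and per-patient rate relate.** Let r be ICAs per patient evaluated and s the negative share. Unnecessary ICAs per patient are U = r × s. If r rises by a fraction g, U falls only if s falls by more than g/(1+g):

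| Rise in ICA use, g | Relative fall in share needed | From 14% to below |
|---|---|---|
| 5% | 4.8% | 13.3% |
| 10% | 9.1% | 12.7% |
| 40% | 28.6% | 10.0% |

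The required relative fall does not depend on the starting share. For the planned effect, the break-even rise in use is 14/6 = 2.33-fold.

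**5. Range over the missing input.** The control's ICA rate per patient evaluated is not in the documents. It is varied here as an assumption, with the cohort held at 21% × 6% = 1.26% and the control share at 14%:

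| Assumed control ICA rate | Control U | Change in U |
|---|---|---|
| 5% | 0.70% | +80% |
| 9% | 1.26% | none |
| 15% | 2.10% | −40% |
| 21% | 2.94% | −57% |
| 30% | 4.20% | −70% |
| 42% | 5.88% | −79% |

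The share comparison is the same, 14% against 6%, in every row. In the other direction, if the share stayed at 14% while ICA use fell from 42% to 21%, U would halve from 5.88% to 2.94% and the share comparison would show no effect.

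**6. What the cohort alone can show.** Under 8.3, patients above 70% stenosis go to ICA whatever the CT-FFR result, so CT-FFR can be set against the ICA result there. At 50-70%, 8.3 orders a new MPI only after a negative CT-FFR. ICAs triggered by a new MPI in that band are therefore CT-FFR-negative by construction.

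**The case against.** The strongest reply is that the plan can be read as per ICA throughout. Section 14.1 is explicitly per ICA, and 6.1 confines the control to cases where testing led to catheterization. The reductions in Sections 10 and 11 are statements of belief about benefit and not endpoints. This stands in part: it makes per ICA the natural choice. It does not remove the wording of 6.2 or the hazard model, which such a control cannot support.

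Four stronger readings are tempting, and the documents do not support them:

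- *The plan ignores CT-FFR accuracy.* It does not. Sections 2, 3.1, 6.2 and 6.4 intend it. What is missing is an analysis in 14.2 that carries it out and separates what triggered each ICA.
- *The pathway can only add ICAs.* Compared with the CCTA/MPI rule in 6.1, Section 8.3 does add some for positive CT-FFR. But the control is not that rule. The footnote in Section 9 says historical practice for borderline disease was discretionary, 8.3 has a prior-MPI branch, and 8.9.1 lets cardiologists use the FFR images. The net direction is unknown. Sections 10 and 15.5 already disclose that a few ICAs may be added.
- *A lower share would at least prove a better PPV from CT-FFR.* The control includes stress-test-only and discretionary referrals from earlier years, so case mix could lower the share. The result would describe the whole pathway.
- *A fall from 14% to 6% would mislead.* It would do so only if ICA use rose more than 2.33-fold.

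**Conclusion.** The concern holds in a limited form. The only historical comparison the planned data allow is the negative share among performed ICAs. Neither unnecessary ICAs per patient evaluated nor a 90-day hazard of the ICA event can be estimated for the control. The share and the per-patient rate can diverge in either direction. The planned effect is fairly robust to this, while smaller effects are not: a 10% rise in ICA use cancels any relative fall in share up to 9.1%.

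This rests on treating a negative ICA as an ICA without need for intervention, as 14.1 in effect does, and on 14.1's 60%, 35%, 14% and 6%. Section 14.1 describes its start value thus: "the false-positive rate of CCTA+CT-FFR was 14"%. Its use as the rate without CT-FFR is therefore itself an assumption. Figure 1 was not available to this review. The matter should be settled before analysis because it determines what the trial may claim.

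**What to change.** (a) In 6.2 and 14.2, define the historical primary comparison as the negative share among performed ICAs in both groups, and drop the 90-day hazard model for it. State that the result describes the yield of ICA under the whole pathway, against a historical referral group that was partly stress-test-only and discretionary. State also that it does not by itself show fewer catheterizations without intervention, or a PPV gain due to CT-FFR.

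(b) In 14.2, add a supportive descriptive table that carries out the per-modality aim of Sections 2, 3.1 and 6.4. It should set CT-FFR result against ICA result within the cohort, by stenosis band and by what triggered the ICA, with exact 95% confidence intervals. List ICAs without a CT-FFR reading (7.6.1) apart. Rest any estimate of avertable ICAs (CT-FFR-negative, ICA-negative) or of disease that would be missed (CT-FFR-negative, ICA-positive) on the band above 70%. Report 50-70% as descriptive only. Do not use a McNemar test or a pooled avertable percentage. Record the ICA trigger if it is not already captured.

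(c) Reconcile 6.1, 8.3 and 9.2. Section 6.1 gives MPI to all patients at 30-100%, while 8.3 and 9.2 give it at 50-70% after a negative CT-FFR. A 70% stenosis falls in one band in 6.1 and in two in 8.3 and 9.2. These points decide which row an ICA belongs to. Which text should prevail is for the investigators.

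**Cost.** Text changes, one table and possibly one data field, with care unchanged. There is still no per-patient historical comparison, and the claim is narrower. Precision is low: 121 ICAs yield about 17 negatives at 14% (121 × 0.14) or 7 at 6% (121 × 0.06), before splitting by band. The 80% power in 14.1 is for a test against a fixed 14%. A two-group comparison with 121 ICAs each has 55% power and needs 220 per group for 80%. The control's size is not stated.
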